#### **Secondary criteria**

##### VAS (neuropathic pain) before and at 2 months after surgery

- The mean difference between the 2 groups (with or without cold application) will be estimated and compared using a linear mixed model taking into account the VAS score measured at baseline and the stratification criterion on the centre.

##### DN4 before installation and at 2 months

- The mean difference between the 2 groups (with or without cold application) will be estimated and compared using a linear mixed model taking into account the DN4 score measured at baseline and the stratification criterion on the centre.

##### EVA (burning sensation) after 30 minutes

- The mean VAS between the 2 groups (with or without cold application) will be estimated and compared using a linear mixed model taking into account the stratification criterion on the centre.

The evolution of the pain at 30 minutes and 1 hour will be represented graphically.

##### Short-term follow-up (7 days)

- The mean NE between the 2 groups (with or without cold application) will be estimated and compared using a linear mixed model taking into account the stratification criterion on the centre.

- The use of cold application during the week following the application will be compared between the 2 groups by a Chi2 test.

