### **Conduct of the study :**

This is a multicentre study on 5 different geographical sites (La Roche sur Yon, Montaigu, Challans, Nantes, Les Sables D'Olonne). It is planned to randomise 100 patients in total. In order to compensate for possible patients who would be included (signed non-objection) but could not be randomised, a maximum of **110 patients will be included**. Enrolment will be completed once the study has reached 100 randomised patients.

Approximately two months before the first Qutenza® patch is applied, the patient is seen in an information consultation by a doctor as part of their treatment at the CETD. On this occasion, a nurse will complete the consultation by presenting the DIDOCAP study and by proposing to the patient to participate.

The patient will go home with the information leaflet. The patient's non-objection can be collected on the day of this consultation or at the latest on the day of the first patch of Qutenza®. The non-objection will be collected and signed by the doctor and/or the nurse.

If the patient refuses, he/she will receive the most appropriate treatment for his/her situation (Qutenza patch® with or without the application of cold, at the discretion of the medical team and according to the patient's choice in accordance with the standard practice of the centres).

If the patient accepts, a randomisation will be performed on the day of the Qutenza patch® (via the e-CRF). The two randomisation groups are :

- **Patient receiving Qutenza® without cold application or**
- **Patient receiving Qutenza® combined with cold application**

At each consultation (2 months before inclusion, on the day of inclusion (patching), at 1 month and at 2 months after patching) the patient will be seen by both a doctor and a nurse.

**Doctor:** The doctor prescribes the Qutenza® patch, and carries out the tracing with the nurse on the day of application in the day hospital. He also prescribes painkillers for the week following the application if necessary.

The doctor sees the patient again at 1 and 2 months.

**Nurse:** The nurse greets the patient, assesses the pain, performs a global evaluation, gives information about adverse events related to the procedure, applies the patch according to the doctor's instructions following the Qutenza® patch use procedure.

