**3. DESCRIPTION OF MEASURES TAKEN TO REDUCE AND AVOID BIAS**

Randomisation will be performed in an open-label fashion, according to 2 groups of patients: one group with cold application and another group without cold application on the Qutenza patch®. The randomisation will be stratified on the centre. It will be carried out according to a 1:1 ratio and will be performed in blocks. Patients will be randomised on the day of application.

Randomisation will be carried out via the Capture System software by connecting to the website: <https://nantes-lrsy.hugo-online.fr/CSOnline/>.

The connection will be carried out thanks to a login, a password and a study number, delivered by the data manager of the CHD Vendée of La Roche sur Yon.

The following information should be filled in:

- First initial of the name,
- First initial of the first name,
- Month and year of birth,
- Compliance with inclusion and non-inclusion criteria (yes/no), -      No opposition to the study collected (yes/no).

Randomisation will be carried out by the investigator after confirmation of the possibility of inclusion in the study and the collection of no objection.

The inclusion number will be assigned automatically during randomisation. An email confirmation will be sent to the person who performed the randomisation and to all the persons concerned at the centre.

The randomisation list will be drawn up by the study methodologist, [name], CHD Vendée before the start of the study. An explanatory guide to randomisation will be available online under Capture System.

The randomisation list will be protected by restricted access and accessible only by the study biostatistician.

4. DURATION OF PARTICIPATION FOR A SUBJECT IN THE RESEARCH AND A DESCRIPTION OF THE TIMING AND DURATION OF ALL TRIAL PERIODS, INCLUDING FOLLOW-UP WHERE APPLICABLE

The duration of a patient's participation will be 2 months from the day of the installation with a delay of up to 3 months depending on the availability and organisation of the service.

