#### **Main criterion**

The primary endpoint was the VAS collected 1 hour after the start of the procedure.

The mean VAS between the 2 groups (with or without cold application) will be estimated and compared using a linear mixed model taking into account the stratification criterion on the centre. The "cold application" criterion will be taken into account as a fixed effect and the centre as a random effect.

The main analysis will be "intention to treat". It may be supplemented by a "per-protocol" analysis. No intermediate analysis is planned.

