## 3. EXPECTED LEVEL OF STATISTICAL SIGNIFICANCE

The significance level is set at 5%.

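### Cold use in the week after the patch is compared by an unstratified Chi2 test, although centre is the randomisation stratum: a small, free improvement in power

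*Combined protocol and SAP*

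**What the plan says.** Section III.3 (measures to reduce bias) fixes the design: "The randomisation will be stratified on the centre", and "It will be carried out according to a 1:1 ratio and will be performed in blocks". The block size is not given. Section III.2 (Conduct of the study) says "This is a multicentre study on 5 different geographical sites", while the Summary counts 4 centres and 5 sites.

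Section VI.1 carries centre into the analysis almost throughout. For the primary VAS, the treatment criterion "will be taken into account as a fixed effect and the centre as a random effect". The 2-month VAS, the 2-month DN4 and the 30-minute VAS also have linear mixed models that include the centre criterion. Under Short-term follow-up (7 days), the pain score is analysed "using a linear mixed model taking into account the stratification criterion on the centre".

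The next bullet under that heading departs from this: home use of cold over the 7 days "will be compared between the 2 groups by a Chi2 test". No other part of the document adds a centre-adjusted analysis for this endpoint, and none gives an effect estimate or interval for it.

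**The concern.** Blocks within centre keep the two arms nearly balanced at each centre. Differences between centres therefore contribute almost nothing to the variance of the arm difference. A pooled Chi2 does not use this: it takes its variance from the overall proportion, which includes the between-centre spread. If centres differ in how often patients use cold at home, that variance is too large, the test rejects too rarely under the null, and a real difference between arms is more likely to be missed.

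Cold use in the week after application is a listed secondary criterion. It may also help a reader interpret the 7-day pain scores, because cooling at home could influence them, although the plan has no analysis linking the two. What is at stake is some power on one secondary comparison, and consistency between how patients were allocated and how the data are analysed.

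**Working it through.** **The plan's own figure.** The only sample-size calculation is for the primary VAS (section VI.2): difference 2, SD 2.8, alpha 5% (two-sided assumed), power 90%.

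n per group = 2 × (1.960 + 1.282)² × 2.8² / 2² = 2 × 10.51 × 7.84 / 4 = 41.2, so 42.

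This reproduces the stated 42. It does not involve the cold-use comparison, for which no power target is given.

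**Inputs for the check.** From the documents: 50 patients per arm, 1:1 allocation in blocks within centre, significance level 5%. Assumed, because the documents do not give them: the rate of home cold use at each site, the split of patients between sites, and the treatment effect.

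**Why the Chi2 becomes conservative.** Let site k have rate p_k, with equal site sizes and overall rate p̄.

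- Variance factor used by the pooled Chi2: p̄(1 − p̄)
- Variance factor that applies when arms are balanced within site: mean of p_k(1 − p_k) = p̄(1 − p̄) − var(p_k)

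For five sites at 30, 40, 50, 60 and 70%:

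- var(p_k) = (0.04 + 0.01 + 0 + 0.01 + 0.04)/5 = 0.02
- ratio of variances = (0.25 − 0.02)/0.25 = 0.92
- the effective critical value rises from 1.96 to 1.96/√0.92 = 2.04, a type I error near 4.1%

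For 20-80%, var(p_k) = 0.045, the ratio is 0.82 and the type I error is near 3.0%. For 10-90%, var(p_k) = 0.08, the ratio is 0.68 and the type I error is near 1.8%. Simulated values run slightly higher because the counts are discrete.

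**Simulation A: five sites of 20 patients, exact balance within site.** 200,000 replicates per scenario, common log odds ratio −1.2 for power, two-sided 5%, neither test continuity-corrected.

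| Control rates across sites | Type I error, Chi2 | Type I error, CMH | Power, Chi2 | Power, CMH |
|---|---|---|---|---|
| all 50% | 0.057 | 0.056 | 0.806 | 0.806 |
| 40-60% | 0.054 | 0.054 | 0.798 | 0.801 |
| 30-70% | 0.047 | 0.049 | 0.764 | 0.781 |
| 20-80% | 0.034 | 0.048 | 0.685 | 0.743 |
| 10-90% | 0.021 | 0.049 | 0.529 | 0.669 |

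The power lost is 0, 0.3, 2, 6 and 14 points. Four strata, or uneven sites of 40/30/10/10/10, give the same pattern.

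**Simulation B: uneven sites of 20, 10, 10, 5 and 5 per arm, odds ratio 1/3.5.**

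- Equal rates: power 84% for both tests.
- Control rates 30-70%: Chi2 type I error about 4.4%. The power loss is about 1 to 3 points, for example 76% against 79%.
- Control rates 15-85%: Chi2 type I error about 2.0 to 2.4%. Power is 58% against 67% in one assignment of rates to sites and 53% against 68% in another, a loss of 9 to 15 points. It depends on which sites have the high rates: with the highest rate at the largest site, power is 72% against 78%.

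**Exact CMH in the layout of simulation B.** Its type I error is about 3 to 4%. Its power is 77-79% with equal rates (planned Chi2 84%), 71% at 30-70% (Chi2 75-76%), and 59% at 15-85% (Chi2 58%, asymptotic CMH 67%).

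**The case against.** The strongest objection is that the premise, sites differing in home cooling, is not in the documents. A reader might infer it from section I.2, which reports no consensus on cooling, or from section III.2, which leaves cooling to the team's discretion for patients who decline the study. Both passages concern cooling while the patch is on, and neither mentions the following week or says that these centres differ. Section V.1 points slightly the other way, since the participating centres already use the same brand of cushion. This objection stands: heterogeneity is an assumption, and the size of the loss is a range rather than an estimate.

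A reader might also conclude that the plan's error rate for this test falls below 5%. That is not true in general. With equal rates the Chi2 rejects about 5.7% of the time under the null, and at 40-60% about 5.4%. It becomes clearly conservative only when site rates are widely spread.

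Finally, the consequence is small. This is one of several secondary criteria with no power target, and the mechanism makes false positives rarer, not more common. This also stands, and it limits the point to an optional improvement. It does not remove the point, because the stratified test loses nothing when sites are alike and gains when they differ.

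**Conclusion.** The point holds as a minor, optional improvement. The analysis of home cold use omits the randomisation stratum that every other comparison in section VI takes into account. Whether this costs anything depends on site differences that the documents do not describe: nothing if rates are equal, about 1 to 3 points of power at 30-70%, and about 9 to 15 points in the main layouts run at an extreme 15-85%. These figures rest on assumed site rates, site sizes and odds ratios of about 1/3.3 to 1/3.5, with arms exactly balanced within site. The planned Chi2 is not invalid, and nothing here affects the primary result or the 42 per group.

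**What to change.** In section VI.1, Short-term follow-up (7 days), replace the Chi2 with an asymptotic Cochran-Mantel-Haenszel test without continuity correction, stratified by centre as defined for randomisation. State whether that means the 4 centres or the 5 sites. Report the common odds ratio or the Mantel-Haenszel risk difference with its 95% CI.

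Do not make an exact version the default. In the layout with two sites of 5 patients per arm, the asymptotic test kept close to its nominal level, whereas the exact test gave up as much power as stratification gained, or more.

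The cost is one line of statistical wording. Centre is already recorded as the randomisation stratum, so no new data, patients or procedures are needed.

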## 2. EXPECTED NUMBER OF PEOPLE TO BE INCLUDED IN THE RESEARCH, AND EXPECTED NUMBER OF PEOPLE IN EACH RESEARCH LOCATION WITH ITS STATISTICAL JUSTIFICATION

Based on retrospective observations carried out at the CETD of the La Roche sur Yon hospital, on average, patients present a VAS pain of 7/10 one hour after application. We would like to reduce this pain to 5/10 (a reduction of 2 clinically relevant points) by applying cold during the application of the Qutenza patch .®

Assuming a decrease of 2 points between the initial VAS of the burn and the VAS at 1H, with a standard deviation of 2.8, an alpha risk of 5% and a power of 90%, 42 patients per group will be required. In order to compensate for possible dropouts, 50 patients per arm, i.e. 100 patients in total, will be randomised.

In addition, in order to also accommodate possible patients who would be included (signed non-objection) but could not be randomised, a maximum of **110 patients will be included**.

Enrolment will be completed once the study has reached 100 randomised patients.

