**Criteria assessed :**

The protocol consists of assessing the intensity of the burning sensation by means of a VAS at 30 minutes and 60 minutes of exposure.

It should be noted that the VAS evaluated before the Qutenza® patch, at 1 month and at 2 months after application concern the patient's neuropathic pain, whereas the VAS at 30 and 60 minutes are the pain related to the burning sensation.

Concomitant treatment(s) received by the patient prior to the application of Qutenza® and in particular those taken on the day of application of the Qutenza® patch will also be collected.

Patients will be reviewed in a medical consultation at 1 month and 2 months after insertion, according to standard practice. This last visit may be carried out at 2 months or at the latest at 3 months after insertion, depending on the organisation and availability of the department.

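### Does the sample size rest on a within-patient fall in burning VAS that is never measured, instead of the between-arm difference that is tested?

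*Combined protocol and SAP*

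**What the plan says.** Section VI.2 describes the same 2 points twice.

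- Its first paragraph reports from retrospective observations that "on average, patients present a VAS pain of 7/10 one hour after application" and sets a target of 5/10 with cold, calling the 2-point reduction clinically relevant.
- The next paragraph begins "Assuming a decrease of 2 points between the initial VAS of the burn and the VAS at 1H, with a standard deviation of 2.8" and continues with "an alpha risk of 5% and a power of 90%, 42 patients per group will be required". The number randomised is then raised to 50 per arm for dropouts.

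Section VI.1 (Main criterion) defines the endpoint as the VAS at 1 hour and says: "The mean VAS between the 2 groups (with or without cold application) will be estimated and compared using a linear mixed model". Cold is a fixed effect and centre a random effect; there is no baseline term.

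Section III.2 (Criteria assessed) schedules the burning VAS at 30 and 60 minutes only. It states that "the VAS evaluated before the Qutenza® patch, at 1 month and at 2 months after application" refer to neuropathic pain.

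**The concern.** The calculation sentence speaks of a fall from an initial burning score to the 1-hour score and attaches the SD of 2.8 to that fall. Three things in the plan do not fit.

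- No initial burning score exists. The only VAS taken before the patch concerns a different pain.
- Burning is not expected to fall over the hour. Section III.1 reports that 70% of first-patch patients had more pain at 1 hour than at 30 minutes.
- The primary test is a comparison of arms at one time point, not a test of change.

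The SD of a change and the SD of a single score are in general different quantities. If 2.8 were the former, the 90% power would not carry over to the primary test, and the trial could be over- or underpowered without the reader being able to tell. No source for 2.8 is given that would settle it.

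**Working it through.** **Inputs.** Difference 2 (7/10 versus 5/10), SD 2.8, alpha 5%, power 90%, all from section VI.2; 1:1 allocation from section III.3. Sidedness is not stated; two-sided is assumed.

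**1. The plan's figure as a between-arm comparison.** n per group = 2 (z₀.₉₇₅ + z₀.₉₀)² SD² / difference² = 2 × (1.960 + 1.2816)² × 2.8² / 2² = 2 × 10.507 × 7.84 / 4 = 41.19, rounded up to 42. This is the stated number. The two-sample t-test gives 43. A one-sided 5% test would give 34, so the two-sided assumption is the one that fits.

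**2. The same inputs as a within-patient change.** n = 10.507 × 7.84 / 4 = 20.6, so 21 patients in total, or 23 by the t-test. Neither gives 42 per group.

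**3. Power if 2.8 is the SD of the 1-hour VAS.** By t-test, 89.9% at 42 per arm and 94.3% at 50 per arm. The allowance from 42 to 50 corresponds to 16% dropout (1 − 42/50), while section VI.4 expects no missing values on this endpoint.

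**4. Power if 2.8 is instead the SD of a change.** With equal variances at both times and correlation ρ, the 1-hour SD is 2.8 / √(2(1 − ρ)). Neither equal variances nor any value of ρ is in the documents; the values below are assumptions.

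| ρ | 1-hour SD | Power, 42 per arm | Power, 50 per arm |
|---|---|---|---|
| 0.3 | 2.37 | 97% | 99% |
| 0.5 | 2.80 | 90% | 94% |
| 0.6 | 3.13 | 82% | 89% |
| 0.7 | 3.61 | 71% | 78% |

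At 50 per arm, power reaches 90% up to a 1-hour SD of about 3.05. Setting 2.8 / √(2(1 − ρ)) = 3.05 gives 2(1 − ρ) = 0.843, so ρ ≈ 0.58. Below that correlation the 90% is kept or exceeded.

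**5. Sensitivity to the SD itself.** At 50 per arm, power is 91.0% for a 1-hour SD of 3.0, 87.2% for 3.2 and 80.8% for 3.5 (assumed values).

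**The case for a change.** The strongest case for acting is that the first paragraph of section VI.2 ties only the effect to the primary test. It gives means, not an SD. The value 2.8 appears once, without a source, in the sentence about change, so a reader who takes that sentence at its word cannot confirm the 90%. Under that reading power at 50 per arm could be as low as 78% for ρ = 0.7. The section also leaves open whether the 7/10 comes only from patients treated without cold: section I.2 mentions a group of 90 at the same centre, half of whom had no cold. One look-up in the sponsor's retrospective data would settle both.

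What stands is that the sentence misdescribes the effect and that the SD lacks a definition and a source. What does not stand is the inference to power. The unfavourable rows need a literal reading that the plan's own arithmetic does not follow, plus equal variances and a correlation above about 0.58. Equal variance is also not the natural case. If the initial score meant the moment of placement, before burning has built up (section I.2 describes it as progressive), that score would plausibly vary little. The SD of the change would then lie close to the 1-hour SD, and 2.8 would serve for both. This is a plausibility argument, not something the documents report.

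**Conclusion.** No change to the plan follows. The clause about an initial score is a clerical slip, most likely a loose reference to the 7/10 seen without cold. The effect in the preceding paragraph, the formula that yields 42 and the primary analysis all describe the same two-sided comparison of mean 1-hour burning VAS between arms. No stated figure is shown to be wrong.

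On that reading power is 89.9% at 42 and 94.3% at 50 per arm, provided 2.8 is the between-patient SD of the 1-hour VAS. That proviso rests on inference, since the plan does not say where 2.8 comes from. Underpowering is not shown, and under the alternative reading power could as well be higher than stated. Endpoint, model, number randomised and the reading of the result are the same whichever way the sentence is worded. A trial report would do well to describe the calculation as 7 versus 5 at 1 hour and to say what the 2.8 is, which is ordinary reporting detail.

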## 3. EXPECTED LEVEL OF STATISTICAL SIGNIFICANCE

The significance level is set at 5%.

## 4. METHOD OF ACCOUNTING FOR MISSING DATA

The number of missing data and the reason for the missing data will be described in each of the treatment groups.

As the endpoint is collected one hour after patching, there will be no missing data on this endpoint.

# **VII RIGHT OF ACCESS TO SOURCE DATA AND DOCUMENTS**

## 1. Access to data

The medical data of each patient will only be transmitted to the organisation of the person responsible for the research or any person duly authorised by the latter under conditions that guarantee their confidentiality.

## 2. Source documents

Where appropriate, the responsible person's home organization may request direct access to the medical file for verification of research procedures and/or data, without breaching confidentiality and within the limits permitted by laws and regulations.

## 3. Data privacy

Persons with direct access shall take all necessary precautions to ensure the confidentiality of information relating to the persons who have access, in particular as regards their identity and the results obtained.

These persons, as well as the investigators themselves, are subject to professional secrecy (according to the conditions defined by articles 226-13 and 226-14 of the penal code). During or after the research, the data collected on the subjects and transmitted by the participants will be made anonymous.

Under no circumstances should the names of the persons concerned or their addresses appear in clear text.

Only the first letter of the subject's name and the first letter of the subject's first name will be recorded, along with the month and year of birth and a coded study number indicating the order of inclusion of subjects.

